#### 6.5. Brief Pain Inventory questionnaire (BPI)

The BPI questionnaire has two sections: pain intensity (4 items) and interference with activities of daily living (7 items). Each item is given a score on a numerical scale from 0 (no pain/interference with activities of daily living) to 10 (worst pain imaginable/maximum impact on activities of daily living).

The results for these 11 items are then used to obtain two overall scores: Pain severity and Pain interference:

- Pain severity: mean of the four pain items.
- Pain interference: mean of the seven interference items.

The data of the BPI scale for the total of patients that complete all the items of the scale will be analyzed. All items of BPI and two overall scores will be described by the mean, median, standard deviation, maximum and minimum.

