The assessment of breakthrough pain intensity will be performed using the scores obtained on the numerical rating scale. A description of the scores will be given using the mean, median, standard deviation, maximum and minimum.

Each of the items on the BPI questionnaire and Alberta scale will be described, using the mean, median, standard deviation and range to describe the continuous variables and frequency distributions and percentages to describe the categorical variables.

The SF-12 quality of life scale consists of 12 items, from which total scores for the physical and psychological components are obtained. The correction methods indicated in the scale's validation manual will be used for the total score for each sub-scale, and the mean, median, standard deviation and range will be presented.

Breakthrough pain in patients with cancer pain will be characterised based on aetiology and pathogenesis, as well as other clinical characteristics (type of breakthrough pain, number of episodes per day, duration and intensity, and pain management). This information will be collected with the tools used for the clinical assessment of breakthrough pain.

Given the special characteristics of the elderly population and patients with multiple myeloma, a sub-analysis of pain characterisation will be performed in patients over 70 years of age and in those with multiple myeloma.

The percentage of patients who present the various profiles/types of breakthrough cancer pain (characterisation/classification) and the causes for the same will be determined.

The percentage of patients with the various profiles/types of breakthrough cancer pain will be given based on demographic characteristics and other clinically significant variables relating to the cancer diagnosis (tumour type, stage, etc.), pain intensity, comorbidities, etc. The quality of life of patients with cancer breakthrough pain will be analysed based on its possible relationship with demographic characteristics and other clinically significant variables related to the cancer or to the breakthrough pain such as aetiology, frequency of episodes, pain intensity, time until peak of pain, crisis duration, cause, etc.

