## 5. PREVALENCE STUDY RESULTS

### 5.1. General considerations

The prevalence study results will be performed in the “prevalence study population”.

As this is an epidemiological study, no imputation on the missing data will be calculated.

Valid percentages will be presented, that is, the real number of observations available in each variable will be used as the denominator. The number of missing data for each variable will be indicated.

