#### 6.4. Breakthrough cancer pain

We will characterize the breakthrough pain based on:

- Etiology (nociceptive, neuropathic or mixed)
- If nociceptive,
  - Somatic nociceptive or visceral nociceptive (question Q2 of Alberta's questionnaire to be completed by physician or nurse).
- Trigger factor of breakthrough pain (spontaneous pain or idiopathic pain / incident pain).
  - If incident pain,
    - Volitional, non-volitional and procedural.
- Location and type of breakthrough pain (BCP type I to IV).
- Pain intensity (Question 3 of BPI scale: Please rate your pain by circling the one number that best describes your pain at its least in the past 24 hours).

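### SAP 6.5 drops a patient from all its BPI results if any one of the 11 items is blank, although each score needs only its own four or seven items

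*SAP*

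**What the plan says.** SAP 6.5 splits the BPI into four pain-intensity items and seven interference items. It states "The results for these 11 items are then used to obtain two overall scores: Pain severity and Pain interference", with the definitions "Pain severity: mean of the four pain items" and "Pain interference: mean of the seven interference items". No item enters both scores.

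The same section then sets the analysis set: "The data of the BPI scale for the total of patients that complete all the items of the scale will be analyzed". The next sentence says what is drawn from it: "All items of BPI and two overall scores will be described by the mean, median, standard deviation, maximum and minimum".

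Other places that bear on the point:

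- Protocol 10.1: "Each of the items on the BPI questionnaire and Alberta scale will be described". It attaches no completion condition.
- SAP 4.1: the characterisation population is every eligible, consented patient. Questionnaire completeness plays no part.
- SAP 6.4: BPI Question 3 is reported as the measure of pain intensity, again without a completion condition.
- SAP 7 and 8: the two BPI scores are tabulated by breakthrough pain type I to IV. Sections 6.4 to 6.8 are repeated for patients over 70, for multiple myeloma and for each of the five specialties.
- SAP 5.1, general considerations for the prevalence study: "the real number of observations available in each variable will be used as the denominator", with missing counts shown and no imputation.

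**The concern.** A blank on an interference item says nothing about the four pain items, yet under SAP 6.5 it removes the patient's severity score. It also removes the answers to the other ten items from the item-by-item description, where full completion serves no scoring purpose. The rule therefore discards data that patients supplied and that protocol 10.1 meant to describe.

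Three things are at stake:

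- The number of patients behind the BPI results falls, most noticeably in the small subgroups of SAP 8.
- BPI Question 3 could appear in 6.4 and in 6.5 with different denominators.
- SAP 6.1 does not ask for missing counts in the characterisation part, so the loss need not be visible in the report.

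**Working it through.** **Inputs from the documents.** 11 BPI items, 4 for severity and 7 for interference (SAP 6.5). 529 patients planned for characterisation (protocol 10.3, SAP 3.6). 60 hematology patients under the competitive-recruitment limits (protocol 7).

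**Assumed input.** The probability q that a given item is blank is not in the documents. The range 0.5% to 5%, with blanks independent across items, is for illustration.

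**Step 1: the base number.** The 529 is used here only as a denominator. It is stated for a 10% characteristic with a 95% interval of ±2.5 points. The plain formula gives 1.96² × 0.10 × 0.90 / 0.025² = 553.2. A finite-population correction with N = 13,200 gives 553.2 / (1 + 552.2/13,200) = 531.0, close to 529. The documents do not mention such a correction, so that route is inferred. Nothing below depends on it.

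**Step 2: patients kept.**

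- All 11 items (SAP rule): 529 × (1 − q)^11
- Four severity items only: 529 × (1 − q)^4
- Seven interference items only: 529 × (1 − q)^7
- One single item: 529 × (1 − q)
- Complete severity score lost only through an interference blank: 529 × [(1 − q)^4 − (1 − q)^11]

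| q per item | All 11 (SAP) | Severity items | Interference items | Single item | Severity score lost needlessly |
|---|---|---|---|---|---|
| 0.5% | 500.6 | 518.5 | 510.8 | 526.4 | 17.9 |
| 1% | 473.6 | 508.2 | 493.1 | 523.7 | 34.5 |
| 2% | 423.6 | 487.9 | 459.2 | 518.4 | 64.3 |
| 3% | 378.4 | 468.3 | 427.4 | 513.1 | 89.9 |
| 5% | 300.9 | 430.9 | 369.4 | 502.6 | 130.0 |

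Example for q = 3%: 0.97^11 = 0.7153 and 0.97^4 = 0.8853, so 529 × (0.8853 − 0.7153) = 89.9.

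**Step 3: a small subgroup.** In hematology at q = 2%, the SAP rule keeps 60 × 0.98^11 = 48.0. Complete severity items keep 60 × 0.98^4 = 55.3, and a single item keeps 60 × 0.98 = 58.8. The relative loss is the same in every subgroup but matters more where n is small.

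**Step 4: dependence between blanks.** Independence is unfavourable to the rule. At the other extreme, a fraction q of patients leaves the whole form blank and everyone else completes it. Then 1 − q of patients are kept under any rule (95% at q = 5%), and the all-items condition costs nothing. Real data would probably lie between the two.

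**Step 5: selection.** If a fraction m is excluded and those patients differ by D points from completers, the completer mean differs from the full mean by m × D. With m = 10% and D = 1 the shift is 0.1 on the 0 to 10 scale; with m = 20% and D = 1 it is 0.2. The documents supply neither m nor D.

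**The case against.** Complete-item scoring is a recognised choice and keeps one denominator across the BPI tables. The BPI is a secondary assessment criterion (protocol 2), its analysis is descriptive, and the primary prevalence result is untouched. Protocol 9.1 plans automatic checks, individual review and queries for incomplete data, so blank rates of 3% to 5% per item may not occur. Overall precision would also change little: with an assumed SD of 2.5, the 95% half-width of a BPI mean is 1.96 × 2.5 / √n, which is 0.21 at n = 529, 0.23 at 474 and 0.25 at 378. All of this stands and limits the size of the point. It does not remove the rule, because protocol 9.1 accepts missing data when a reason is given.

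The BPI user guide (SAP Appendix 2) is a separate document, not seen here, and may hold its own missing-item rule. However, the SAP defers to the manual for SF-12 scoring, whereas for the BPI it writes out its own full-completion condition.

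A reader might also infer more than the documents support:

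- *That SAP 6.5 contradicts SAP 5.1.* The available-observations rule in 5.1 is written for the prevalence study. The BPI belongs to section 6, so this is a difference of approach, not a contradiction.
- *That every single-item BPI result is affected.* Question 3 as reported in SAP 6.4 carries no completion condition and may escape.
- *That the sickest patients are the ones removed.* It is plausible that patients with poor function leave activity items blank, but no passage shows it.
- *That the rule undermines the 529.* That number was set for a 10% proportion, not for BPI means.

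**Conclusion.** The point holds on the SAP's own wording. The rule in 6.5 is stricter than either score requires, has no purpose for single items, and adds a condition that protocol 10.1 does not contain.

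Its size is unknown because no item-missing rate is given. Under independent blanks of 0.5% to 5% per item, it removes 5.4% to 43.1% of patients from the 6.5 results. Requiring only the four severity items would lose 2.0% to 18.5% from the severity score. These are illustrative figures, and clustering of blanks or successful queries would reduce them. Selection bias is a possibility, not a demonstrated effect. The consequence is confined to secondary descriptive results and is most noticeable in the small subgroups of SAP 8. The change is still worth making, because it recovers data already collected at almost no cost.

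**What to change.** Replace the completion sentence in SAP 6.5 with a rule to this effect:

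- Describe each BPI item on all available answers, showing n and the number missing.
- Score pain severity when its four items are answered, and pain interference when its seven items are answered, each regardless of the other section.
- Allow partial scoring within a section only if the BPI user guide attached to the SAP provides for it, and cite that provision. The protocol and SAP text supports no threshold of its own.
- Apply the same rule in SAP 7 and 8, and state whether Question 3 in 6.4 uses the same set of patients as in 6.5.

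The cost is a short SAP amendment and minor programming. The number of patients will differ slightly between BPI tables, which the reported n makes clear.

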#### *Appendix 2: BPI User guide*

#### 6.6. SF-12 questionnaire

The SF-12 quality of life scale consists of 12 items, from which total scores for the physical and psychological components will be obtained. The correction methods indicated in the scale's validation manual will be used for the total score for each sub-scale, and the mean, median, standard deviation and range will be presented.

#### *Appendix 3. SF-12 questionnaire*

#### 6.7. Karnofsky PS

The analysis of Karnofsky PS will be described by the distribution of frequencies and percentages.

### 6.8. Alberta Breakthrough Pain Assessment Tool

A different Alberta scale will be collected for each type of breakthrough cancer pain (most bothersome breakthrough pain, second most bothersome breakthrough pain and third most bothersome breakthrough pain) presented by the patient, up to a maximum of 3 questionnaires).

Each of the items on the Alberta scale will be described separately by type of breakthrough cancer pain (most bothersome breakthrough pain, second most bothersome breakthrough pain and third most bothersome breakthrough pain), using the mean, median, standard deviation and range to describe the continuous variables and frequency distributions and percentages to describe the categorical variables.

#### *Appendix 4. Alberta Breakthrough Pain Assessment Tool*

## 7. RELATIONSHIP BETWEEN BCP AND DEMOGRAPHIC AND OTHER CLINICALLY SIGNIFICANT VARIABLES

We will provide for the different types of breakthrough pain (BCP type I to IV) the number and percentage or mean (SD) and median (range), as applicable, the following variables:

- Age
- Gender
- Type of cancer
- Current stage (I-III vs IV)
- Previous treatments (yes/no)
- Current treatments
  - Surgery (yes/no)
  - Chemotherapy (yes/no)
  - Radiotherapy (yes/no)
- Comorbidities
- BPI results: Pain severity and Pain interference.
- Etiology (nociceptive, neuropathic or mixed)
- Trigger factor of breakthrough pain (spontaneous pain or idiopathic pain / incident pain).
- If incident pain, then volitional, non-volitional and procedural.
- Questions 4a, 4b, 7 and 8 from Alberta questionnaire.

We will provide the mean, standard deviation, median and range of the physical and psychological components of the SF-12 questionnaire (quality of life of patients with cancer breakthrough pain) according to the following variables:

- Age (<70years; ≥ 70years)
- Gender
- Type of cancer
- Current stage (I-III vs IV)
- Previous treatments (yes/no)

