#### Secondary:

- To estimate the annual incidence of patients with breakthrough cancer pain relative to the population of cancer patients with or without pain seen in participating practices over one month.
- To characterize breakthrough pain in patients with cancer pain based on medical history, etiology and pathogenesis, tumour type, location, stage, comorbidities, etc., as well as other clinical characteristics (type of breakthrough pain, number of episodes per day, duration and intensity, and baseline pain management). This information will be collected with the tools used for the clinical assessment of breakthrough pain.
- To assess the prevalence of each of the different causes of pain.
- To determine the percentage of patients who present each of the different profiles/types of breakthrough cancer pain (characterization/classification) and classify them based on the results obtained in the Alberta and BPI questionnaires.
- To determine the percentage of patients who present each of the profiles/types of breakthrough cancer pain and assess possible relationships with demographic characteristics and other clinically significant variables related to the cancer such as diagnosis, pain intensity, comorbidities, etc.
- To assess the quality of life of patients with breakthrough cancer pain and its possible relationship with demographic characteristics and other clinically significant variables related to the cancer or to the breakthrough pain such as etiology, frequency of episodes, pain intensity, time until peak of pain, crisis duration, cause, etc.
- To assess the performance status of patients using the Karnofsky scale in order to know the degree of general wellbeing and ability to cope with activities of daily living presented by the patients studied.

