## “Characterisation and Epidemiology of Breakthrough Cancer Pain in Spain”

planned sites, will be interviewed on the prevalence of breakthrough cancer pain. This sample will enable us to detect the prevalence of breakthrough pain with a 95% confidence interval and precision of  $\pm 1\%$ .

For the assessment of the secondary objective, i.e., characterizing the breakthrough pain based on etiology, underlying pathology and other clinical characteristics, if it is considered the detection of common characteristics in at least 10% of patients in our population to be representative, it will be necessary to recruit 529 patients in order to detect said characteristics with a 95% confidence interval and precision of  $\pm 2.5\%$ .

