## 6. CHARACTERIZATION BREAKTHROUGH PAIN ANALYSIS

### 6.1. Demographic and baseline description. General considerations

The demographic and baseline description will be performed for all "analyzed patients".

Given the descriptive nature of the study, the statistical methodology used will be based primarily on an exploratory analysis of the data through the calculation of descriptive parameters.

The continuous variables will be summarized in a table showing the mean, median, standard deviation and maximum-minimum range and the categorical variables will be presented as absolute frequencies and percentages.

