### 8. SUBANALYSIS

Given the special characteristics of the elderly population and patients with multiple myeloma, a sub-analysis of pain characterization (points 6.4 to 6.8 of this statistical analysis plan) will be performed in the following samples:

- Patients over 70 years of age.
- Patients with multiple myeloma.

Additionally a sub-analysis of pain characterization (points 6.4 to 6.8 of this statistical analysis plan) will be performed in the following samples:

- Patients included in Medical Oncology Departments.
- Patients included in Hematology Departments.
- Patients included in Radiotherapeutic Oncology Departments.
- Patients included in Pain Units.
- Patients included in Palliative Care Units.

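### SAP 7 describes SF-12 by unadjusted one-way summaries only, so the quality-of-life objective can be answered only as crude description, with no uncertainty reported for differences

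*SAP*

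**What the plan says.** Protocol section 3 and SAP 3.5 set the same secondary objective: "To assess the quality of life of patients with breakthrough cancer pain and its possible relationship with demographic characteristics and other clinically significant variables". Protocol 10.1 takes it up with "The quality of life of patients with cancer breakthrough pain will be analysed based on its possible relationship with demographic characteristics" and names no method.

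The method appears in SAP 7: "We will provide the mean, standard deviation, median and range of the physical and psychological components of the SF-12 questionnaire". The breakdown variables follow as a list: age below or from 70, gender, cancer type, current stage (I-III against IV), previous treatments, three current treatments, comorbidities, aetiology, trigger, incident subtype, pain location, BCP type and four Alberta questions. Each is used singly. No difference, interval, correlation, model or two-way table for SF-12 appears in the readable text.

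Specialty is not on that list. It enters through SAP 8: "Additionally a sub-analysis of pain characterization (points 6.4 to 6.8 of this statistical analysis plan) will be performed in the following samples", the samples being the five specialties. SF-12 is point 6.6, so it is described within each specialty. The section 7 breakdowns are not repeated there.

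By contrast, SAP 5 (primary and secondary objective analyses) attaches a 95% CI to the prevalence estimates. SAP 6.1 states the general approach: "the statistical methodology used will be based primarily on an exploratory analysis of the data through the calculation of descriptive parameters".

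**The concern.** The objective is about a relationship, and the outputs are separate group summaries. Two things a reader needs are absent.

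- **Uncertainty of a difference.** An SD describes the spread between patients. It does not say how precisely two group means have been compared, and neither do the median and range.
- **Confounding.** Patients are recruited by specialty, with a fixed number per investigator and competitive specialty quotas if recruitment falls short (Protocol 6.3 and 7). Some SAP 7 factors could plausibly follow specialty, for example current radiotherapy with Radiotherapeutic Oncology, or cancer type with Hematology. A one-way table cannot separate a factor from the specialty or stage that travels with it.

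At stake is the reading of one secondary objective: raw gaps between groups, some of them small, may be taken as relationships.

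**Working it through.** **Sample size.** SAP 3.6 says "it will be necessary to recruit 529 patients in order to detect said characteristics with a 95% confidence interval and precision of" ±2.5%, for a characteristic present in 10% of patients. The plain formula gives n = 1.96² × 0.10 × 0.90 / 0.025² = 553.2, rounded up to 554. A finite-population correction on the 13,200 patients of the prevalence part gives 553.2 / (1 + 552.2/13,200) = 531.0, within 2 patients of 529. The documents do not state that correction, so it is inferred. The relevant fact is that 529 rests on the precision of a proportion and not on any comparison of SF-12 means.

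**Precision of a difference in SF-12 means.** The documents give no SF-12 SD. Assume 10 points per component, with a range of 8 to 12, and complete SF-12 data on all 529. The half-width is 1.96 × SD × √(1/n₁ + 1/n₂).

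| Split of 529 | n₁, n₂ | SD 8 | SD 10 | SD 12 |
|---|---|---|---|---|
| 50/50 | 265, 264 | 1.36 | 1.70 | 2.05 |
| 80/20 | 423, 106 | 1.70 | 2.13 | 2.55 |
| 90/10 | 476, 53 | 2.27 | 2.84 | 3.41 |

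The splits are illustrative, because the documents do not give the distribution of any SAP 7 factor. The formula also ignores similarity between patients at the same site, which would widen the interval for factors that vary mainly between sites.

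**Number of comparisons.** The SF-12 list in SAP 7 has 18 entries, counting comorbidities once: 18 × 2 components = 36. If no relationship were real, 36 × 0.05 = 1.8 comparisons would on average fall outside a nominal 95% limit. If the comparisons were independent, the chance of at least one is 1 − 0.95³⁶ = 0.84. Multi-level factors and separate comorbidities would raise the count.

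**Confounding, as an illustration only.** Suppose a stratum (a specialty or a stage group) shifts SF-12 by 5 points (assumed; range 3 to 8), and holds 60% of one comparison group and 20% of the other (also assumed). With no true effect of the factor, the crude difference is 5 × (0.60 − 0.20) = 2.0 points (3 × 0.40 = 1.2 to 8 × 0.40 = 3.2). That is similar in size to the half-widths above, and a one-way table would not reveal it.

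**The case against.** The strongest reply is that the study is declared descriptive and the objective speaks only of a possible relationship. Neither document promises inference or adjusted effects for SF-12, and tabulating it by factor is a legitimate descriptive reading. A reader might infer that the objective cannot be answered at all. The documents do not support that: it can be answered as crude description.

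A reader might also infer that no difference could be told from chance. That goes too far as well. If group sizes are printed, mean, SD and n give a crude interval by simple arithmetic. Whether they will be printed cannot be checked, because the SAP Appendix 1 table index is redacted and the visible table templates cover categorical variables only.

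Third, SF-12 will be seen by stage (SAP 7) and by specialty (SAP 8), so the association of each with quality of life will be reported. The link between those two and the other factors is plausible, but no figure in the documents shows it.

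These points narrow the concern without closing it. A difference with a CI is an estimate and not a test, and the SAP already gives intervals for prevalence within the same descriptive approach. Summaries by stage and by specialty, each taken alone, do not adjust any other factor for them.

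**Conclusion.** The gap holds in a limited form. For SF-12 the plan supplies unadjusted one-way summaries, so the relationship objective is met only as crude description. Uncertainty of differences is not reported, and possible confounding by specialty or stage cannot be examined from the planned outputs. Confounding is a possibility left unexamined here; it has not been demonstrated.

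The unreported sampling error is about 1.7 points (1.4 to 2.0) for an even split and 2.8 (2.3 to 3.4) for a 90/10 split. This rests on the assumed SD of 10 (8 to 12), 529 complete SF-12 records and no allowance for site. The judgement rests on the readable SAP text. It is an inexpensive improvement to a secondary objective and corrects no error; the primary prevalence analysis is unaffected.

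**What to change.** In SAP 7, report for each factor the difference in mean SF-12 physical and psychological score with a 95% CI.

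- **Contrasts.** Compare two-level factors directly. Compare multi-level factors, such as cancer type, against a named reference category. If a patient can have more than one BCP type, use a separate yes/no indicator for each type, since the groups would overlap.
- **Crude and adjusted.** Give each difference crude, and again from a linear model adjusted for age, sex, specialty and current stage, with a separate category for patients without a I-IV stage.
- **Clustering.** Use standard errors clustered by site; 66 sites are planned.
- **Labelling.** Call the results exploratory, do no hypothesis testing, and state the number of comparisons.

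The cost is SAP wording and some programming. All the variables are already collected. The downside is more figures to present, and some of the roughly 36 intervals would exclude zero by chance (about 1.8 expected if nothing were real), which is why the count should be stated. The adjusted estimates remain exploratory. If the sponsor prefers pure description, the minimum is to say in SAP 7 that the comparisons are descriptive and unadjusted, and to word the objective to match.
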